10.3.2.11 Hospital Anxiety and Depression Scale

The Hospital Anxiety and Depression Scale (HADS) is a Likert-scale tool widely used to detect states of anxiety and depression in a general hospital setting (24). The tool consists of 14 items that assess the subject's anxiety (7 items) and depression (7 items) during the last week. Each question is scored from 0 to 3, with high scores indicating a poor state. The HADS will be completed electronically on the device supplied to the trial site according to the SoP (Section 4) and is included in the investigator trial file.

10.3.2.12 Treatment Satisfaction Questionnaire for Medicine

The Treatment Satisfaction Questionnaire for Medicine (TSQM) v. II is a generic questionnaire assessing subjects' satisfaction with the treatment (30). The tool consists of 11 items addressing effectiveness, side effects, convenience and overall satisfaction. The TSQM will be completed electronically on the device supplied to the trial site according to the SoP (Section 4) and is included in the investigator trial file.

10.4 Safety assessments

10.4.1 Vital signs

Vital signs (resting blood pressure, pulse, and body temperature) must be assessed according to the SoP (Section 4). Vital signs will be measured in supine position following at least 5 minutes rest.

If an abnormal vital sign at screening is considered by the investigator to be clinically significant, it will be up to the investigator's discretion if the subject should be randomised into the trial (respecting exclusion criterion no. 26).

In case of abnormal findings, the vital sign measurement can be repeated approximately 15 minutes later with subjects resting in a supine position to verify the first measurement. Should the repeated measurement result in a normal value, the measurement must be repeated once more. If the third measurement verifies the second (normal) value, the first measurement should be considered as false. If the third measurement confirms the first measurement (abnormal) the second measurement will be considered as false. Only the last value measured and considered as correct will be recorded in the eCRF.

Trial ID: LP0162-1325	Date: 14-Aug-2018	Version: 4.0
		Page 75 of 169

Clinically significant abnormal vital signs at the (first) screening visit will be documented as medical history in the eCRF (refer to Appendix 4D for further details). If an abnormal vital sign at any other visit than the first screening visit is considered by the investigator to be clinically significant, it will be reported as an AE in accordance with the principles for data entry (Appendix 4D).

10.4.2 Physical examination

A thorough physical examination of the subject including whole body inspection of the skin and auscultation of heart, lungs and abdomen; palpation of the abdominal organs and basic neurological status must be performed according to the SoP (Section 4).

If an unacceptable abnormal finding is identified during the physical examination at the screening visit, the subject must not be randomised into the clinical trial (respecting exclusion criterion no. 26).

Refer to Appendix 4D for principles for data entry into the eCRF.

10.4.3 Digital ECG

A single 12-lead resting digital ECG will be recorded after the subject has been supine for at least 5 minutes at the visits indicated in the SoP (Section 4).

A pre-evaluation of the ECGs will be performed by the investigators to evaluate immediate subject safety. At a minimum, date of ECG collection will be recorded in the source documents.

The ECG data will be transferred to a central ECG service company for central evaluation. A cardiologist at the ECG service company will analyse and interpret the ECG data. The ECG service company will provide ECG evaluation reports to the trial sites.

The investigator must evaluate all abnormal ECG results ('clinically significant' or 'not clinically significant') and sign and date. The investigator has the final decision on the clinical significance of ECG abnormalities. If a result is abnormal at the screening visit and considered by the investigator to be clinically significant, it will be up to the investigator's discretion if the subject should be enrolled into the trial (respecting exclusion criterion no. 26); if such a subject is enrolled, the investigator will provide a justification in the medical record. Refer to Appendix 4D for principles for data entry in the eCRF.

Trial ID: LP0162-1325	Date: 14-Aug-2018	Version: 4.0
		Page 76 of 169

Test dummy transmissions will be undertaken prior to trial conduct to ensure that transmissions can be made and that date and time settings are correctly set.

The collection and transmission of ECG data will be described in a separate ECG manual.

10.4.4 Pregnancy test

A serum pregnancy test must be taken at the screening visit in female subjects of child-bearing potential as described in the SoP in Section 4.

A urine pregnancy test (human chorionic gonadotropin; dipstick) must be performed at the trial site at baseline prior to randomisation in female subjects of child-bearing potential. The test must be repeated every 4 weeks as shown in the SoP in Section 4.

Note that pregnant subjects must discontinue IMP immediately (Section 9.8.1).

10.4.5 Laboratory testing

The following safety samples will be analysed by a central laboratory: chemistry, haematology, serology, and serum pregnancy (Panel 13). Urine samples will be tested at the trial site with a dipstick; if abnormal, a urine sample will be sent to the central laboratory for further analysis.

A laboratory manual will be provided to the sites that specifies the procedures for collection, processing, storage, and shipment of samples, as well as laboratory contact information specific to this trial.

Samples for laboratory testing will be collected according to the SoP (Section 4).

Panel 13 Central laboratory testing	Panel 13	Central	laboratory	testing
-------------------------------------	----------	---------	------------	---------

Chemistry	Haematology
Sodium	Erythrocytes
Potassium	Hematocrit
Creatinine	Hemoglobin
Urea nitrogen	Erythrocyte mean corpuscular volume
Calcium	Erythrocyte mean corpuscular haemoglobin
Alkaline phosphatase	concentration
Aspartate aminotransferase	Leukocytes
Alanine aminotransferase	Neutrophils, neutrophils/total cells
Gamma glutamyl transferase	Lymphocytes, lymphocytes/total cells
Bilirubin ¹	Monocytes, monocytes/total cells
Lactate dehydrogenase	Eosinophils, eosinophils/total cells
Cholesterol	Basophils, basophils/total cells
LDL cholesterol	Thrombocytes
HDL cholesterol	Serology
Triglycerides	Hepatitis B virus surface antigen ⁴
Glucose (non-fasting)	Hepatitis B virus surface antibody ⁴
Albumin	Hepatitis B virus core antibody ⁴
Protein	Hepatitis C virus antibody ⁴
Tryptase ²	HIV-1 antibody ⁴
	HIV-2 antibody ⁴
	Immunoglobulin E ⁵
Urinalysis ³	Serum pregnancy test (females only) ⁴
Protein	Choriogonadotropin beta
Glucose	
Ketones	
Occult blood	
Leukocytes	
Nitrite	

1) If bilirubin is above upper limit of normal, direct and indirect bilirubin will also be measured.

2) Only measured in case of suspected anaphylaxis (Section 9.2).

 Urine samples will be tested at the trial site (dipstick). In case of abnormal dipstick results, a urine sample will be sent to the central laboratory for microscopic examination (leukocytes, erythrocytes, and casts).

Measured at screening only.

5) Not measured at screening.

HDL, high density lipoprotein; LDL, low density lipoprotein.

The investigator must evaluate all results outside the reference range ('clinically significant' or 'not clinically significant') and sign and date. The signed and dated version will be filed with the investigator's trial documentation. Clinically significant abnormal tests must be repeated to confirm the abnormality.

Trial ID: LP0162-1325	Date: 14-Aug-2018	Version: 4.0
		Page 78 of 169

The central laboratory will provide results in conventional units to trial sites in the US and in SI units to trial sites in Europe and Asia; results that are transferred to the trial database will be in conventional and SI units.

Handling, storage, destruction and shipment instructions are provided in a separate laboratory manual.

If a screening laboratory result is abnormal and of clinical significance, it will be at the investigator's discretion to decide if the subject should be enrolled into the trial (respecting exclusion criteria no. 26, 27, and 28).

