Panel 2 Schedule of trial procedures: screening and initial treatment period (continued)

	Scree	ening ¹				I	nitial treat	ment perio	d			
Visit	11	2	3	4	5	6	7	8	9	10	112	12 ³
Week	-6	-2	0	2	4	6	8	10	12	14	15	16
Investigator assessments of efficacy (Section												
EASI	х		х	x	х	x	Х	Х	х	x		Х
SCORAD	х		х	х	х	х	Х	Х	х	х		Х
Subject assessments of efficacy (Section 10.	3.2)											
eDiary training		х										
eDiary completion9		<- ==										
POEM and DLQI			х	x	х	x	х		х			х
EQ-5D-5L and HADS			х		х		х		х			х
SF-36 and WPAI-GH			х				Х					Х
TSQM				x								х
Safety assessments (Sections 10.4 and 11)												
Vital signs	х		X ⁸	X ⁸	X ⁸	x	х	х	х	x		X ⁸
Physical examination	х		х				Х					Х
ECG	х		х				Х					Х
Serum pregnancy test	х											
Urine pregnancy test			х		х		х		х			х
Hepatitis B, C and HIV	х											
Serum chemistry, haematology, and IgE	X ¹⁰		х		х		х		х			Х
Urinalysis	Х		Х				х					Х

Trial ID: LP0162-1325	Date: 14-Aug-2018	Version: 4.0
		Page 20 of 169

Panel 2 Schedule of trial procedures: screening and initial treatment period (continued)

	Scree	ning ¹				Iı	nitial treat	ment perio	d			
Visit	11	2	3	4	5	6	7	8	9	10	112	12 ³
Week	-6	-2	0	2	4	6	8	10	12	14	15	16
Safety assessments (Sections 10.4 and 11)	afety assessments (Sections 10.4 and 11)											
Pharmacokinetics				Х	Х					х	X ²	х
ADA			Х		Х							х
Adverse events	х	х	х	х	х	х	х	х	х	х		х
Other assessments (Section 10.5)												
Skin swabs (S. aureus)			Х									х
Skin swabs (microbiome) ¹¹			х				х					х
Serum biomarkers (small panel)			х		Х		х					х
Serum biomarkers (large panel) ¹¹			х		х		х					х
Skin biopsies ¹¹			X ¹²		х							х
Photography ¹¹			х	х	х	х	х	х	х	х		Х

 For subjects who do not require a wash-out, visits 1 and 2 will be combined and screening will be reduced to 2 weeks; hence, these subjects will only attend visit 2 (Week -2) which will include all assessments shown under Week -6. Similarly, for subjects who only require a 2-week wash-out, screening visits 1 and 2 will be combined (Week -2). The screening period has a maximum duration of 6 weeks.

2) At Week 15, subjects will only have a blood sample drawn. No assessments that require trial personnel will be performed. Collection of AEs and reporting of concomitant medication and procedures will occur at the following trial visit.

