5.1 Atopic dermatitis

Atopic dermatitis (AD) is a chronic inflammatory skin disease that may affect up to 20% of children and up to 10% of adults. In its severe form, AD is characterised by widespread skin lesions, intractable itch, as well as enhanced susceptibility to bacterial, viral, and fungal skin infections (1-4). AD is associated with a substantial patient burden that typically includes poor quality of life, sleep disturbance, and reductions in work productivity (5).

Treatment recommendations for AD include topical therapies, the main being topical corticosteroids (TCS). Unfortunately, TCS and topical calcineurin inhibitors (TCIs) have limited efficacy in patients with moderate-to-severe disease. TCS and non-biologic systemic therapies are all associated with toxicities with long-term use (6-8).

AD is characterised by an activated T-helper-2 (Th2) pathway with increased skin expression of key Th2 cytokines including interleukin (IL)-13 (9, 10). The expression of IL-13 is increased in lesional skin compared to non-lesional skin, and the proportion of CD4⁺ and CD8⁺ cells expressing IL-13 is upregulated in AD patients compared to individuals without AD (9, 11).

IL-13 acts on keratinocytes to release C-C motif chemokine 22 (CCL22) and recruit more IL-13 expressing Th2 cells, decrease differentiation, and contribute to decreased barrier function (12). IL-13 also drives immunoglobulin E (IgE) production and contributes to mast cell activation status and, once allergen cross-links IgE on the cell surface, drives histamine release and induces itch (13, 14). Indeed, itch is a key issue in AD, which drives significant mechanical damage to the skin and further facilitates allergen and pathogen entry.

All of these effects together drive and exacerbate the disease phenotype. A review of the available preclinical literature from mouse and human ex vivo models suggests IL-13 as a, if not the, central mediator of the AD skin phenotype. Indeed, there is evidence that blocking the IL-4 receptor (which is part of the receptor complex which also binds IL-13) with the monoclonal antibody dupilumab leads to clinical improvement in AD subjects (15).

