9.3.1 Blinding

This is a double-blinded trial in which tralokinumab and placebo are visually distinct from each other. Neither the subject nor any of the investigator or LEO staff who are involved in the treatment or clinical evaluation and monitoring of the subjects will be aware of the treatment received. The packaging and labelling of the IMPs will contain no evidence of their identity.

Since tralokinumab and placebo are visually distinct and not matched for viscosity, IMP will be handled and administered by a qualified, unblinded HCP at the site who will not be involved in the management of trial subjects and who will not perform any of the assessments.

In the event that the treatment allocation for a subject becomes known to the investigator or other study staff involved in the management of trial subjects, LEO must be notified immediately.

Should an issue arise with the IMP (e.g., damaged kit or syringe that has been assigned to a subject prior to administration, or any other unexpected event with the kit or syringe [e.g., a malfunction during IMP administration]), the unblinded HCP at the site will contact the clinical research associate (CRA) to determine whether any specific actions are required.

The trial site will maintain a written plan detailing which staff members are blinded/unblinded and the process of IMP administration used to maintain the blind.

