## 6.7.8 Biomarkers

The small panel biomarkers; periostin, DPP4, hBD2, TARC, IL-13, IL-17, IL-22, and IgE will be summarized and listed. Other potential biomarkers from the small panel will be presented in a separate report.

As described in the protocol the large panel biomarkers will be presented in a separate report.

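### Post-baseline IgE falls within the laboratory results sent to sites, and nothing masks it from those who score efficacy: a possible, unquantified clue to treatment that is cheap to remove

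*Protocol*

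**What the plan says.** **Sampling.** The row "Serum chemistry, haematology, and IgE" in the schedule of procedures (Protocol Section 4) is marked at Weeks 0, 4, 8, 12 and 16 in Panel 2, and every 4 weeks from Week 20 to Week 52 in Panel 3. Panel 13 places IgE under serology with the footnote "Not measured at screening", so the series starts at baseline and every later value is post-dose.

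**Release and review.** Protocol Section 10.4.5 calls the Panel 13 tests safety samples. It says "The central laboratory will provide results in conventional units to trial sites in the US", and in SI units to sites in Europe and Asia. It adds: "The investigator must evaluate all results outside the reference range". The investigator signs and dates that review, and clinically significant results are repeated. Appendix 4D turns clinically significant findings after the first screening visit into adverse events.

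**Biology.** Section 5.1 states that "IL-13 also drives immunoglobulin E (IgE) production". Section 5.2 states that tralokinumab binds IL-13 and blocks its interaction with its receptors. SAP Section 6.7.8 groups IgE with the exploratory markers: "The small panel biomarkers; periostin, DPP4, hBD2, TARC, IL-13, IL-17, IL-22, and IgE will be summarized and listed".

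**Blinding.** Section 9.3.1 begins "Neither the subject nor any of the investigator or LEO staff who are involved in the treatment or clinical evaluation" and goes on to say that they will not know the treatment received. Its measures are an unblinded professional who handles and injects the product, immediate notice to the sponsor if an allocation becomes known, and a written site plan of blinded and unblinded staff. Section 10.1 keeps those who score efficacy away from dosing and asks for one investigator to do all evaluations of a given subject.

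**The concern.** Masking can fail through data as well as through the look of a syringe. Here the plan measures repeatedly a marker that, by its own account, lies downstream of the drug's target. It routes that marker through the reports that sites receive and does not say who may see it.

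The ratings exposed to such a clue carry the trial. IGA 0/1 and EASI75 at Week 16 are the primary endpoints, and SCORAD, whose extent and intensity parts are scored by the investigator, is a secondary endpoint. IGA and EASI also decide who is re-randomised at Week 16 and who moves to open-label treatment during maintenance, and that move counts as non-response at Week 52. Rescue treatment is at the investigator's discretion (Section 9.7) and also makes a subject a non-responder. A suspicion about the arm could therefore act through the score or through the decision to rescue.

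**Working it through.** **1. Tracing IgE through the text**

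| Step | Source | Finding |
|---|---|---|
| Drawn after dosing | Panels 2 and 3 | Yes, every 4 weeks |
| Central-laboratory test | Panel 13 | Yes, under serology |
| Results to sites | Section 10.4.5 | General rule, no IgE exception |
| Investigator review | Section 10.4.5 | All out-of-range values |
| Out-of-range IgE foreseeable | Appendix 5 | Raised serum IgE is a minor diagnostic feature |
| Linked to drug target | Sections 5.1, 5.2 | Yes, by mechanism |
| Raters kept from dosing | Sections 9.3.1, 10.1 | Yes |
| Raters kept from laboratory reports | Both documents | Not stated |

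No sentence names IgE as released. Release follows from its place in Panel 13 together with the general rule.

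**2. Which values can reach which rating**

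Section 10.1 puts efficacy scoring before laboratory sampling at each visit. The Week 16 sample therefore cannot affect the Week 16 score. The values that could be known by then are baseline and Weeks 4, 8 and 12, if reports return within 4 weeks (turnaround is not given). For the Week 52 rating, the maintenance values that could be known are Weeks 20 to 48, eight in all.

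**3. The plan's own figure, for context**

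Section 12.1 gives more than 99% power for IGA 0/1 at 30% versus 10% with 585 and 195 subjects.
- Pooled rate: (195 × 0.10 + 585 × 0.30)/780 = 0.25.
- Null SE: √(0.25 × 0.75 × (1/195 + 1/585)) = 0.0358; critical difference 1.96 × 0.0358 = 0.0702.
- Alternative SE: √(0.09/195 + 0.21/585) = 0.0286.
- Power: Φ((0.20 − 0.0702)/0.0286) ≈ Φ(4.53), above 0.9999.

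The stated figure reproduces. Power does not protect against rating bias.

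**4. How strong a clue could be (assumption)**

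The documents give no size, timing or variability for any IgE change. Suppose the arms differ by d standard deviations in IgE change, with normal distributions and equal spread. The chance of a correct guess, averaged equally over the two arms, is Φ(d/2).

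| d | 0 | 0.25 | 0.5 | 1 | 2 |
|---|---|---|---|---|---|
| Correct guess | 50% | 55% | 60% | 69% | 84% |

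The range starts at no information at all, and nothing in the documents places the trial within it.

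**5. What a rating bias would do (assumption)**

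Suppose no true effect, 10% response on placebo, and b percentage points of bias in favour of tralokinumab. The chance of a two-sided significant result uses the same SE formulas as step 3. For b = 2, the pooled rate is 0.115, the critical difference is 0.0517 and the alternative SE is 0.0253. The upper tail is 1 − Φ((0.0517 − 0.02)/0.0253) ≈ 0.106, and with the lower tail the total is about 0.108.

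| b (points) | 0 | 1 | 2 | 3 | 5 | 8 |
|---|---|---|---|---|---|---|
| P(significant) | 5% | 6% | 11% | 18% | 41% | 78% |

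This shows how sensitive the test is to bias. It does not estimate the bias in this trial.

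**The case against.** The case on the other side is substantial.

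- **The release sentence concerns units.** It does not name IgE, and the laboratory manual, which is not among the documents, might mask it. This stands as a limit. The manual's described scope (collection, processing, handling, storage, destruction, shipment, contacts) does not mention masking, but that does not settle what it contains.
- **A reader might infer that the laboratory report reveals the arm.** The documents do not support that. They give a mechanism, not an observed fall in IgE, and listing IgE as a biomarker does not show that it separates the arms. Raters also see the skin response every two weeks, which is itself a clue.
- **Rater and laboratory reviewer may be different people.** The protocol uses the word investigator for both and never says they are the same person. Equally, it requires no separation.
- **Other safeguards exist.** Section 9.3.1 requires notification and a written blinding plan. Sections 10.3.1.1 and 10.3.1.2 require IGA and EASI to be scored on current condition. Scoring precedes sampling. These reduce the exposure but do not cover IgE from earlier visits.
- **A reader might infer that IgE serves no purpose at the site**, since it is absent from the stopping rules in Section 9.8.1 and from SAP Table 2. That goes too far: the review duty and the adverse-event rule apply to every Panel 13 result.
- **The planned effect is large.** If 4 of the assumed 30 points were bias (a figure with no source in the documents), 26% versus 10% has a critical difference of 0.0671, an alternative SE of 0.0281 and power Φ((0.16 − 0.0671)/0.0281) ≈ Φ(3.3), still over 99%. The planned conclusion would survive; the estimate would be inflated.

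**Conclusion.** The gap is real and modest. As written, post-baseline IgE belongs to the results that sites receive and investigators review, and neither document keeps it from the people who score efficacy. It is a possible clue to treatment whose strength cannot be stated from the documents.

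The point rests on three assumptions: that the general release rule covers IgE, that the laboratory manual does not already mask it, and that sites do not separate raters from laboratory review on their own initiative. For the clue to matter, IgE must also shift detectably on tralokinumab by Week 12 or during maintenance, which the documents do not address.

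A reader might go further and conclude that the blind is broken, or that the primary result is biased by some number of points in favour of tralokinumab. Neither follows: no IgE effect size, guess rate or misclassification rate is given, so the tables above are illustrations only. This is a cheap improvement, not a threat to the primary analysis that the documents demonstrate.

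**What to change.** State in Protocol Sections 9.3.1 and 10.4.5, and in the laboratory manual, that post-baseline IgE is withheld from sites, assessors and blinded sponsor staff until unblinding and is sent only to the database. Report all other safety analytes as now.

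Add a matching exception for IgE to the out-of-range review in Section 10.4.5 and the adverse-event rule in Appendix 4D, or assign IgE review to someone who does not rate efficacy. If the laboratory manual already masks IgE, one cross-reference in Section 9.3.1 or 10.4.5 closes the point.

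The SAP is dated 20 May 2019 and cites a data cut-off of 11 April 2019 (Section 6.8.2), so withholding can no longer protect ratings already made. Where results have been released, document who had access and when, and disclose this in the trial report.

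The cost is a reporting setting at the central laboratory, a few sentences of text and a small exception to the review rule. The downside is that investigators do not see IgE during the blinded periods.
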